9.2 SAMPLE SIZE DETERMINATION

9.2.1 Sample Size Considerations for the Dose-Escalation Study

The ability of the study to identify safety events can be expressed in terms of the probability of observing 1 or more event of interest (e.g., AEs) within each arm. With the sample size $n=6$ in each arm, there is over a 90% chance to observe at least 1 AE if the true rate is at least 0.319 and over a 90% chance to observe no AE if the true rate is no more than 0.017. With $n=18$ over 3 dose arms, there is over a 90% chance to observe at least 1 AE if the true rate is no less than 0.121 and over a 90% chance of observing no AE if the true rate is no more than 0.005. Probabilities of observing 0 or more than 1 AE within a group are presented in Table 3 for a range of possible true event rates.

Table 3. Probability (Pr) of events for different safety scenarios within an arm ($n=6$ or 18).

True event rate	n=6		n=18	
	Pr(0)	Pr(>1)	Pr(0)	Pr(>1)
0.005	0.970	0.000	0.914	0.004
0.01	0.941	0.001	0.835	0.014
0.02	0.886	0.006	0.695	0.050
0.035	0.808	0.017	0.527	0.130
0.05	0.735	0.033	0.397	0.226
0.1	0.531	0.114	0.150	0.550
0.15	0.377	0.224	0.054	0.776
0.2	0.262	0.345	0.018	0.901
0.3	0.118	0.580	0.002	0.986

9.2.2 Sample Size Considerations for the Efficacy Study

The efficacy study is designed to evaluate protective efficacy (PE) of CIS43LS at each dose by testing the null hypothesis,

Abbreviated Title: Anti-malaria MAb in Mali

Version Date: October 13, 2022

H0: protective efficacy $\leq 0\%$,
 versus the alternative hypothesis,
 H1: protective efficacy $> 0\%$,
 where PE is 1 minus the ratio of the infection rate under CIS43LS over the infection rate under placebo.

The sample size considerations are based on the power of rejecting H0 over a range of possible protective efficacy and infection rates under placebo. Assuming a drop-out rate of 10%, Table 4 presents the power under a 2-sided significance level of 0.025. With 110 subjects enrolled in each arm, the trial has at least 80% power in each comparison to claim protective efficacy of CIS43LS if the underlying efficacy is greater than or equal to 0.5 and the infection rate under placebo is no less than 0.4.

Table 4. Power for efficacy evaluation under a 2-sided type I error rate of 0.025.

Sample size per arm	Infection rate under placebo	Protective efficacy	Power
100	0.4	0.4	52
	0.4	0.5	76
	0.4	0.6	92
	0.5	0.4	69
	0.5	0.5	90
	0.5	0.6	98
	0.6	0.4	84
	0.6	0.5	97
	0.6	0.6	100
	0.7	0.4	95
110	0.4	0.5	80
	0.4	0.6	94
	0.5	0.4	74
	0.5	0.5	93
	0.5	0.6	99
	0.6	0.4	88
	0.6	0.5	98
	0.6	0.6	100
	0.7	0.4	96
	0.7	0.5	100
	0.7	0.6	100

Abbreviated Title: Anti-malaria MAb in Mali

Version Date: October 13, 2022

Sample size per arm	Infection rate under placebo	Protective efficacy	Power
120	0.4	0.4	61
	0.4	0.5	84
	0.4	0.6	96
	0.5	0.4	78
	0.5	0.5	95
	0.5	0.6	99
	0.6	0.4	91
	0.6	0.5	99
	0.6	0.6	100
	0.7	0.4	98
	0.7	0.5	100
	0.7	0.6	100

Table 5 presents the minimum detectable difference between a CIS43LS arm and a placebo arm in terms of the AE rate based on a two-sided proportion test with type I error rate of 0.025.

Table 5. Minimum detectable difference in adverse event rate in arms receiving monoclonal antibody (MAb) or placebo under a 2-sided type I error rate of 0.025.

Sample size within each arm (#)	Event rate (in placebo) (%)	Detectable with 80% power		Detectable with 90% power	
		Difference (%)	Event rate (in MAb) (%)	Difference (%)	Event rate (in MAb) (%)
100	0.1	9.1	9.2	11.6	11.7
	0.5	9.8	10.3	12.3	12.8
	1.0	10.5	11.5	13.0	14.0
	2.0	11.6	13.6	14.2	16.2
	5.0	14.1	19.1	16.8	21.8
110	0.1	8.4	8.5	10.6	10.7
	0.5	9.0	9.5	11.3	11.8
	1.0	9.7	10.7	12.0	13
	2.0	10.8	12.8	13.2	15.2
	5.0	13.2	18.2	15.7	20.7
120	0.1	7.7	7.8	9.8	9.9
	0.5	8.4	8.9	10.5	11.0
	1.0	9.0	10.0	11.2	12.2
	2.0	10.2	12.2	12.3	14.3

Abbreviated Title: Anti-malaria MAb in Mali

Version Date: October 13, 2022

Sample size within each arm (#)	Event rate (in placebo) (%)	Detectable with 80% power		Detectable with 90% power	
		Difference (%)	Event rate (in MAb) (%)	Difference (%)	Event rate (in MAb) (%)
	5.0	12.5	17.5	14.9	19.9

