2.3.2 Known Potential Benefits

Subjects in the dose-escalation study will not directly benefit from study participation, since the study is too early in the year to be expected to provide protection during the malaria transmission season. In the efficacy study, subjects may not receive direct health benefit from study participation. Depending on whether CIS43LS confers protective efficacy, subjects receiving a sufficient dose of CIS43LS may experience some protection against Pf infection during part or all of the malaria transmission season.

In the future, others may benefit from knowledge gained in this study that may aid in the development of malaria prevention.

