4.3 JUSTIFICATION FOR DOSE

The doses used in this study were selected based off preclinical data and will complement the data generated in the ongoing phase 1 VRC study, which tested the dose range included in this protocol. The doses used in the efficacy study (10 mg/kg and 40 mg/kg IV) will complement the data generated in the ongoing phase 1 VRC study. The 40-mg/kg dose was derived from 1) efficacy data from the challenge studies performed in mice showing that the protective concentration of antibody *in vivo* is between 10-200 µg/mL in 2 different mouse models of malaria infection; and 2) PK data from nonhuman primate studies with CIS43LS and prior clinical experience in healthy adults with human MAbs targeting HIV (i.e., VRC01, VRC01LS, and VRC07-523LS) and ebolavirus (MAb114) at the same dose. The addition of the 10-mg/kg dose was based on more recent PK data from the phase 1 VRC study. Extrapolating PK data from the 5-mg/kg and 20-mg/kg groups in the phase 1 VRC study, we estimate that 10 mg/kg

Abbreviated Title: Anti-malaria MAb in Mali

Version Date: October 13, 2022

will give an *in vivo* concentration of approximately 90 µg/mL at 3 months (mid-malaria season) and approximately 30 µg/mL at 6 months (end of malaria season). The *in vivo* concentration of CIS43LS at the time of CHMI in the 9 protected subjects in the phase 1 VRC study ranged from 50-500 µg/mL.

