9.4.4 Efficacy Analyses

The primary efficacy endpoint (efficacy study primary endpoint) is the incidence of malaria infection defined as blood smear–positive Pf infection through 24 weeks after administration. The secondary efficacy endpoint is the incidence of malaria infection as determined by RT-PCR. The efficacy analyses will be MITT.

The primary efficacy analysis will be based on time to the first infection. The survival patterns will be described by Kaplan-Meier curves for each arm and compared by the logrank test across different arms. The protective efficacy of the study product will be estimated by the hazard ratio from the Cox proportional hazards model. These analyses will be carried out by R packages that account for interval censoring: package “interval” for deriving a nonparametric maximum likelihood estimation based on the Kaplan-Meier survival curve and logrank test, and package “icenReg” for Cox proportional hazards regression. To address the heterogeneity of the study population, a Cox regression with regressors other than the study arm will be additionally performed to account for potential differences among participants. The regressors will include time of enrollment and possibly those covariates that are significantly different between the study product arms and the placebo arm in spite of randomization.

The secondary efficacy analysis will be based on the proportion of infection. The proportions of infection will be estimated for each arm and compared across arms based on Kaplan-Meier estimates along with 95% confidence intervals via R package “bpcp.” This estimation accounts

Abbreviated Title: Anti-malaria MAb in Mali

Version Date: October 13, 2022

for right censoring and the comparison should be equivalent to Fisher's exact test in case of no censoring. Though not accounting for interval censoring, the Kaplan-Meier estimates are appropriate as the interest is on infection at 24 weeks only.

The Holm method will be adopted to address the issue of multiplicity in comparing the 2 dose arms against the placebo.

The above analyses will apply to both the primary and the secondary efficacy endpoints.

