To assess the association of CIS43LS concentration with protection, we will perform a Cox proportional hazards regression for the time to the first infection with CIS43LS concentration as a time-varying covariate. A logistic regression analysis will be additionally performed to model the infection rate as a function of CIS43LS concentration via the method of generalized estimating equation to account for repeated measures.

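### Protective efficacy is defined as 1 minus a ratio of infection proportions but reported as 1 minus a Cox hazard ratio, and the 24-week proportions have no named contrast

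*Combined protocol and SAP*

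**What the plan says.** Section 9.2.2 is the only place that defines PE. It does so within the statement of the null and alternative hypotheses: "PE is 1 minus the ratio of the infection rate under CIS43LS over the infection rate under placebo". Table 4 gives power over placebo infection rates of 0.4 to 0.7 and PE of 0.4 to 0.6.

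Section 9.4.4 makes time to first infection the primary analysis, with a logrank test, and then says: "The protective efficacy of the study product will be estimated by the hazard ratio from the Cox proportional hazards model". An additional Cox model adds baseline regressors but no treatment effect that varies with time.

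The secondary analysis in 9.4.4 is on proportions: "The proportions of infection will be estimated for each arm and compared across arms based on Kaplan-Meier estimates", with 95% confidence intervals. The plan defends ignoring interval censoring there because "the Kaplan-Meier estimates are appropriate as the interest is on infection at 24 weeks only". It names no effect measure for that comparison and does not call it PE. Both analyses apply to the smear and the RT-PCR endpoints.

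Three other places bear on whether the effect is constant over the season. Section 4.3 projects the 10 mg/kg concentration at about 90 µg/mL "at 3 months (mid-malaria season) and approximately 30" µg/mL at 6 months. Section 2.3.2 allows for "some protection against Pf infection during part or all of the malaria transmission season". Section 9.4.6 models "time to the first infection with CIS43LS concentration as a time-varying covariate".

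**The concern.** One name, protective efficacy, covers two quantities. The hypotheses and Table 4 concern the share of infections over the season that is prevented. The planned estimate is a relative reduction in the instantaneous risk of first infection. When infection is common the two are far apart, and the hazard-ratio version is the larger whenever the antibody protects.

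The quantity in the hypotheses has its ingredients in the secondary analysis but no specified estimate and no specified interval. A reader who takes the reported PE at its section 9.2.2 meaning would credit the antibody with more prevented infections than occurred. A single 24-week hazard ratio also cannot show whether protection differed between early and late season.

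**Working it through.** **1. Which scale is Table 4 on?** Inputs from section 9.2.2: 110 per arm, 10% drop-out (0.9 × 110 = 99), two-sided alpha 0.025, placebo rate 0.40, PE 0.5 (so 0.20 on antibody).

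Two-proportion test with pooled variance under the null, mean proportion 0.30, z = 2.241:

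- null standard error √(2 × 0.30 × 0.70 / 99) = 0.0651
- alternative standard error √((0.40 × 0.60 + 0.20 × 0.80) / 99) = 0.0636
- power = Φ((0.20 − 2.241 × 0.0651) / 0.0636) = 80.2%, against 80% stated

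The same formula matches all 31 Table 4 rows checked, with a largest gap of 0.5 points. A continuity-corrected test without drop-out also fits, and it too is on proportions. A hazard-ratio (Schoenfeld) calculation gives 82.9% for this row and comes within 2 points on only 20 of the 31. Reading 'rate' as cumulative proportion is therefore an inference, but a strong one.

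**2. How far apart are the two quantities under exact proportional hazards?** With p0 and p1 the 24-week proportions, HR = ln(1 − p1) / ln(1 − p0). For PE = 50%, p1 = p0 / 2:

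| Placebo p0 | p1 | HR | 1 − HR | Excess over 50% |
|---|---|---|---|---|
| 0.4 | 0.20 | 0.437 | 56.3% | 6.3 points |
| 0.5 | 0.25 | 0.415 | 58.5% | 8.5 points |
| 0.6 | 0.30 | 0.389 | 61.1% | 11.1 points |
| 0.7 | 0.35 | 0.358 | 64.2% | 14.2 points |

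In reverse, a Cox figure of 50% at p0 = 0.4 is a PE of 1 − (1 − 0.6^0.5) / 0.4 = 43.6%; at p0 = 0.7 it is 35.4%.

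In participants, at p0 = 0.7 and PE 50%, 110 recipients yield 110 × 0.35 = 38.5 infections. Reading 64.2% as PE would imply 110 × 0.7 × 0.358 = 27.6.

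**3. Intervals.** In simulated trials with no waning (110 per arm, 10% drop-out, true PE 50%), the Cox 95% interval contains that PE in about 92% of trials at p0 = 0.4 and 63% at 0.7. An interval on 1 minus the ratio of Kaplan-Meier probabilities contains it in about 95%.

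**4. Would declining concentration widen the gap?** This needs a concentration-effect curve, which the documents do not give. Assume, for 10 mg/kg, HR = E / (E + C), with C log-linear through 90 µg/mL at week 12 and 30 at week 24, a constant placebo hazard and p0 = 0.7. E is the half-effect concentration.

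Section 2.2.1 reports 70%-100% protection in mice at 10-200 µg/mL. Setting E / (E + 10) = 0.30 gives E ≈ 4.3.

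| E (µg/mL) | Cox 1 − HR | PE as defined | Total gap |
|---|---|---|---|
| 4.3 (fits mouse data) | 94.8% | 91.0% | 3.8 points |
| 30 | 75.1% | 60.7% | 14.4 points |
| 50 | 65.8% | 48.7% | 17.1 points |
| 100 | 51.2% | 33.2% | 18.0 points |

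Most of each total is the scale difference from step 2. For E = 50, a PE of 48.7% under proportional hazards is already 1 − ln(1 − 0.7 × 0.513) / ln(0.3) ≈ 63%, so waning itself adds about 3 points. For E = 100 the same sum gives 47.6%, so about 4 points; for E = 4.3 it gives 94.6%, so 0.2.

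**The case against.** One minus the hazard ratio is a common efficacy measure, and section 9.4.4 says openly that it is used. The Cox interval misses the section 9.2.2 quantity because it is an interval for something else, which is not a modelling error. Kaplan-Meier curves and 24-week proportions by arm are planned, so a reader could form the ratio by hand, and section 9.4.6 relates risk to concentration over time. At a placebo rate of 0.4, where the sample size is anchored, the discrepancy is small against sampling error. Section 4.1's 68%-90% seasonal infection is for adults who start PCR-negative, and the documents give no smear-based rate.

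All of this narrows the point. It does not remove it, because none of the planned analyses is specified to give PE as defined with an interval, or an effect by period.

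Two stronger readings are tempting and do not hold:

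- **That the plan projects waning efficacy.** Section 4.3 projects concentration, for 10 mg/kg only. Its 6-month value of 30 µg/mL lies below the levels seen "in the 9 protected subjects in the phase 1 VRC study ranged from 50-500" µg/mL but inside the 10-200 µg/mL protective range in mice. Section 2.2.2.1 reports protection about 9 months after 40 mg/kg. Half-effect values of 30-100 µg/mL imply only 9%-25% protection at 10 µg/mL, well short of the mouse data, though mouse data may not carry over to people.
- **That the Cox scale makes the dose arms look closer.** If 40 mg/kg gives four times the concentration (E = 50, p0 = 0.7), the arms are 21 points apart by Cox and 29 by PE as defined. As ratios the order reverses: hazard ratios 0.342 and 0.131 are 2.6-fold apart, risk ratios 0.513 and 0.219 are 2.3-fold apart. No efficacy test between doses is planned.

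**Conclusion.** The point holds as a minor one about the estimand and its label. The reported PE would not be the PE in the hypotheses. It would exceed it by about 6 to 14 points at a PE of 50% across Table 4's placebo range, with no waning assumed. This rests on reading 'infection rate' as a cumulative proportion, which Table 4 strongly supports.

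The 10 mg/kg projection makes a changing hazard ratio possible but does not establish it. At a placebo proportion of 0.7 the total gap could be anywhere from about 4 to 18 points, depending on an unknown concentration-effect curve.

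A reader might also infer that the trial is mis-sized or its tests invalid. It is not: with no effect at any time, both ratios equal 1, and Table 4 is already on the proportion scale. Type I error, power and sample size stand.

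**What to change.** Keep the logrank test, the Cox model and their ranking. In section 9.4.4:

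1. For each dose against placebo, and for both smear and RT-PCR, report 1 minus the ratio of 24-week Kaplan-Meier infection probabilities with its confidence interval, and name it as the estimate of the PE in the section 9.2.2 hypotheses.
2. Label the Cox figure as 1 minus the hazard ratio, and note that Table 4 is on the proportion scale.
3. As a descriptive supplement, report hazard ratios for two prespecified periods, for example to day 84 and after it. Report them whatever a proportional-hazards test shows: in the E = 50 example at placebo 0.7, a two-period test has only about 38% power.

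The cost is a few extra estimates per dose arm from data already collected, with no change to visits, Table 4, the Holm procedure or the sample size. The headline PE will be somewhat lower. Its interval may be slightly wider: 29.9 against 27.6 points in the same example.

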9.3 POPULATIONS FOR ANALYSES

The following datasets will be considered in study analyses:

- Intention-to-treat (ITT) analysis dataset will include all subjects that receive assignment and will be analyzed according to the initial randomization assignment.
- Modified intention-to-treat (MITT) analysis dataset will include all randomized subjects that receive the study intervention and will be analyzed according to the initial randomization assignment.
- Per-protocol analysis dataset will include all randomized subjects that receive the study intervention consistent with the initial randomization assignment and complete the scheduled visits, and will be analyzed according to the initial randomization assignment. In cases where subjects receive an intervention other than the one randomly assigned, an as-treated analysis will be additionally performed according to the actual intervention received.

9.3.1 Evaluable for Toxicity

All subjects will be evaluable for toxicity from the time of their first treatment with CIS43LS or placebo.

9.3.2 Evaluable for Objective Response

Not applicable.

9.3.3 Evaluable Non-Target Disease Response

Not applicable.

9.4 STATISTICAL ANALYSES

9.4.1 General Approach

In general, descriptive statistics will be tabulated by treatment arm for endpoints of interest. This will include point estimates (mean, geometric mean, median, or proportions) and their respective 95% confidence intervals. Formal comparisons will use standard methods, contingency tables for categorical variables, t-tests for comparing means if data follow a normal distribution or geometric means if data after log transformation follow a normal distribution, or nonparametric analogs for comparing medians. Unless specified in the subsequent sections, comparisons will be two-sided with type I error rate of 0.05.

Abbreviated Title: Anti-malaria MAb in Mali

Version Date: October 13, 2022

Missing data will be considered as “missing completely at random” provided missing data is modest (e.g., <10%). We will examine the “missing completely at random” assumption if missing data is more than 10%. If the assumption does not hold, missing data will be handled under the “missing at random” assumption (that is, missingness depends only on observed variables) via methods such as multiple imputation and inverse propensity weighting. To handle the possibility of “missing not at random,” a sensitivity analysis will be performed by imputing missing binary observations with the observed proportion in the opposite arm. A secondary sensitivity analysis will be considered by imputing missing binary observations as failures.

Randomization: In the efficacy study, randomization will be 1:1:1 allocation to the 2 CIS43LS arms and the placebo arm. To limit the number of dropouts before vaccination, randomization and CIS43LS administration will occur as close in time as possible.

9.4.2 Analysis of the Primary Endpoints

Analysis for the primary endpoint for safety and tolerability is described in section [9.4.5](#).

Analysis for the primary efficacy endpoint, protective efficacy with Pf infection determined by blood smear, is described in section [9.4.4](#).

9.4.3 Analysis of the Secondary Endpoints

Analysis of the secondary efficacy endpoint, with Pf infection determined by RT-PCR, is described in section [9.4.4](#).

Analyses of the secondary endpoints for the PK of CIS43LS and the association of CIS43LS concentration with Pf infection risk are described in section [9.4.6](#).

9.4.4 Efficacy Analyses

The primary efficacy endpoint (efficacy study primary endpoint) is the incidence of malaria infection defined as blood smear–positive Pf infection through 24 weeks after administration. The secondary efficacy endpoint is the incidence of malaria infection as determined by RT-PCR. The efficacy analyses will be MITT.

The primary efficacy analysis will be based on time to the first infection. The survival patterns will be described by Kaplan-Meier curves for each arm and compared by the logrank test across different arms. The protective efficacy of the study product will be estimated by the hazard ratio from the Cox proportional hazards model. These analyses will be carried out by R packages that account for interval censoring: package “interval” for deriving a nonparametric maximum likelihood estimation based on the Kaplan-Meier survival curve and logrank test, and package “icenReg” for Cox proportional hazards regression. To address the heterogeneity of the study population, a Cox regression with regressors other than the study arm will be additionally performed to account for potential differences among participants. The regressors will include time of enrollment and possibly those covariates that are significantly different between the study product arms and the placebo arm in spite of randomization.

The secondary efficacy analysis will be based on the proportion of infection. The proportions of infection will be estimated for each arm and compared across arms based on Kaplan-Meier estimates along with 95% confidence intervals via R package “bpcp.” This estimation accounts

Abbreviated Title: Anti-malaria MAb in Mali

Version Date: October 13, 2022

for right censoring and the comparison should be equivalent to Fisher's exact test in case of no censoring. Though not accounting for interval censoring, the Kaplan-Meier estimates are appropriate as the interest is on infection at 24 weeks only.

The Holm method will be adopted to address the issue of multiplicity in comparing the 2 dose arms against the placebo.

The above analyses will apply to both the primary and the secondary efficacy endpoints.

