1. To determine whether ADA to CIS43LS can be detected in sera of recipients at specific timepoints throughout the study. 2. To assess for IgG1 allotypes and allotype-specific effects on CIS43LS PK.	1. Measurement of ADA to CIS43LS in sera of recipients. 2. Assessment of IgG1 allotypes and allotype-specific effects on CIS43LS PK. 3. Characterization of the cellular immune response to CIS43LS.	1. ADA to CIS43LS may impact the PK and activity of CIS43LS. 2. Subject IgG1 allotype may impact the PK and activity of CIS43LS.

Abbreviated Title: Anti-malaria MAb in Mali

Version Date: October 13, 2022

OBJECTIVES	ENDPOINTS	JUSTIFICATION FOR ENDPOINTS

3. To explore and characterize the cellular immune response to CIS43LS.
 
4. To determine if the efficacy of CIS43LS is specific to certain Pf parasite genotypes at the CSP locus.
 
5. To explore the impact of pre-existing parasitemia on the protective efficacy and PK of CIS43LS.
 
6. To explore the impact of pre-existing CSP antibodies on the protective efficacy and PK of CIS43LS.
	
4. CSP genotyping of parasites isolated from study subjects.
 
5. Pre-existing parasitemia detected by microscopic examination of thick blood smears or RT-PCR before CIS43LS infusion.
 
6. Pre-existing CSP-specific antibodies measured in sera collected before CIS43LS infusion.
	
3. CIS43LS-induced cellular immune responses may be associated with Pf infection risk.
 
4. CIS43LS efficacy may be specific to certain Pf parasite genotypes at the CSP locus.
 
5. Pre-existing parasitemia may impact the protective efficacy and PK of CIS43LS.
 
6. Pre-existing CSP-specific antibodies may impact the protective efficacy and PK of CIS43LS.

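### The primary logrank test and Cox hazard ratio are unadjusted; naming enrollment Pf status as a fixed covariate could recover some power, by an amount the documents do not let us fix

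*Combined protocol and SAP*

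**What the plan says.** Section 9.4.4 bases the primary efficacy analysis on time to first smear-positive Pf infection through 24 weeks. For the test it says: "The survival patterns will be described by Kaplan-Meier curves for each arm and compared by the logrank test across different arms". For the estimate: "The protective efficacy of the study product will be estimated by the hazard ratio from the Cox proportional hazards model". No stratum or covariate is named for either. A Cox model with further regressors is run in addition. It always contains time of enrollment; other covariates are possible entrants, and only when they differ significantly between the product arms and placebo. Holm's method covers the two dose comparisons.

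The efficacy schedule (section 1.3.2) takes a blood smear and a dried blood spot for RT-PCR at the enrollment visit and again on day 0. Randomization is on day 0, so the enrollment result precedes it.

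Section 3 gives this variable an exploratory role (objective 5), with the endpoint "Pre-existing parasitemia detected by microscopic examination of thick blood smears or RT-PCR before CIS43LS infusion". Section 9.4.11 describes only the parasite sieve analysis, and section 9.4.9 marks subgroup analyses as not applicable, so no method for objective 5 is set out.

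On power, section 9.2.2 states that "the trial has at least 80% power in each comparison to claim protective efficacy of CIS43LS" when the "underlying efficacy is greater than or equal to 0.5 and the infection rate under placebo is no less than 0.4".

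**The concern.** A covariate measured before randomization can be used in the primary analysis without disturbing the type I error. If it predicts the outcome, a stratified or adjusted time-to-event test has more power than an unadjusted one. Here the sample is already collected from everyone, and the protocol itself says that pre-existing parasitemia may bear on protective efficacy.

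The only route by which section 9.4.4 lets enrollment status into a model is a significant difference between arms. In a randomized trial such a difference arises by chance, and its significance says nothing about whether the variable predicts infection. A useful covariate could therefore be left out and a useless one let in.

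What is at stake is efficiency in the less favorable cells of Table 4. With 110 per arm, power is 80% at placebo rate 0.4 and efficacy 0.5, and 74% at 0.5 and 0.4.

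**Working it through.** **Step 1: reproduce the plan's figure.** Inputs from section 9.2.2: 110 per arm, 10% drop-out, placebo rate 0.4, efficacy 0.5, two-sided alpha 0.025 ("Table 4 presents the power under a 2-sided significance level of 0.025"). Efficacy is defined there as a ratio of rates ("where PE is 1 minus the ratio of the infection rate under CIS43LS over the infection rate under placebo"), so the antibody-arm rate is 0.4 x (1 - 0.5) = 0.2. Evaluable per arm: 0.9 x 110 = 99. Mean rate: 0.3. Critical value: z = 2.241.

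Power = Phi{[0.4 - 0.2 - z x sqrt(2 x 0.3 x 0.7/99)] / sqrt[(0.4 x 0.6 + 0.2 x 0.8)/99]}
= Phi[(0.2 - 2.241 x 0.0651)/0.0636] = Phi(0.850) = 80.2%.

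The plan states 80. The same formula agrees with all 19 Table 4 rows tested, to within about half a point. Table 4 is therefore an unadjusted two-proportion calculation.

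**Step 2: the planned test at the same point.** Under proportional hazards, rates of 0.2 and 0.4 imply a hazard ratio of ln(0.8)/ln(0.6) = 0.437. Schoenfeld's formula with 99 x (0.4 + 0.2) = 59.4 expected events gives 82.9%. Simulation of the plain logrank gives 80.9% to 81.8%. The planned test delivers what Table 4 promises.

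**Step 3: stratify on enrollment status.** The documents give neither the prevalence q of Pf infection at enrollment nor the hazard ratio g for later infection in enrollment-positive against enrollment-negative subjects. Both are assumptions here: q = 10%, 25%, 50% and g = 1 to 5.

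Setup: 99 per arm, exponential event times, follow-up scaled to 1. The hazard is lambda for negatives and g x lambda for positives. In each arm lambda solves (1 - q)(1 - exp(-lambda)) + q(1 - exp(-g x lambda)) = 0.4 (placebo) or 0.2 (antibody), so the overall 24-week rates stay at the plan's values. There were 20,000 trials per setting. Monte Carlo standard error of one power figure: sqrt(0.8 x 0.2/20,000), about 0.3 point.

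Stratified minus plain logrank power, in percentage points:

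| Prevalence q | g = 1 | g = 1.5 | g = 2 | g = 3 | g = 5 |
|---|---|---|---|---|---|
| 10% | -0.2 | 0.0 | +0.5 | +2.1 | +5.7 |
| 25% | -0.3 | +0.2 | +1.2 | +3.8 | +8.7 |
| 50% | -0.2 | +0.2 | +1.6 | +3.5 | +6.3 |

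The simulation uses continuous event times, not the visit-based interval censoring of the trial.

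**Step 4: what this is worth in subjects.** In the Step 1 formula, 81.2% power needs 102 evaluable per arm and 83.8% needs 108, against 99 for 80%. So the gains at q = 25% correspond to about 102 - 99 = 3 subjects per arm at g = 2 and 108 - 99 = 9 at g = 3.

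**Step 5: a higher placebo rate.** With 110 per arm and placebo rate 0.7, the lowest Table 4 entry is 96% (efficacy 0.4), so no change could add more than 100 - 96 = 4 points to that figure. A separate simulation (3,000 trials per setting, 13 grouped visits, prevalence 30% or 50%) puts power at about 97% either way and the gain at no more than 2 points.

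**The case against.** The strongest reply is that nothing is wrong with the plan. An unadjusted logrank test in a randomized trial controls the type I error, and which of the adjusted and unadjusted analyses is primary is a legitimate choice. That stands.

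Several stronger readings might be inferred, and the documents support none of them:

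- *That power is certainly lost.* It is lost only if enrollment status is prognostic, and no section gives that association. At a hazard ratio of 2 or less the gain is under 2 points.
- *That status is the baseline value of the outcome, so a high correlation can be presumed.* All subjects receive artemether-lumefantrine at enrollment to clear blood-stage infection before infusion (section 8.2.1), and the endpoint concerns infection found afterwards (sections 2.2.3.3 and 4.1). Status is at most a marker of exposure or susceptibility.
- *That the 80% is overstated.* It reproduces, and it is a floor for placebo rates of 0.4 or more. Section 4.1 cites 68% to 90% infection over a season in adults who were PCR negative beforehand, without saying whether by smear or PCR. If smear incidence is near 0.7, little is left to gain. Holm's second step also tests at 0.05, so 0.025 is conservative for that comparison.
- *That the unadjusted hazard ratio is biased.* The arm-only and covariate-conditional hazard ratios are different estimands; the difference between them is not an error.
- *That the plan ignores the variable.* It is in exploratory objective 5 and could enter the additional Cox model.

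What survives is narrower: the variable is available before randomization, the plan considers it relevant, and its only route into the efficacy models of section 9.4.4 is chance imbalance.

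**Conclusion.** The point holds as an efficiency suggestion; it identifies no error. Type I error control and the stated power are sound. Prespecifying enrollment Pf status costs at most about 0.3 point of power if the variable is uninformative. At the 0.4/0.5 design point it returns 0.5 to 1.6 points at a prognostic hazard ratio of 2, 2.1 to 3.8 at 3 and 5.7 to 8.7 at 5. These figures rest on an assumed prevalence of 10% to 50%, the assumed hazard ratios, proportional hazards and continuous event times. The range cannot be narrowed from the documents, and the gain falls to about 2 points or less if the placebo rate is near 0.7. The asymmetry between a very small cost and a possible moderate gain is the case for acting.

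**What to change.** In section 9.4.4:

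- Name enrollment Pf status (positive or negative) as a fixed covariate in the primary icenReg Cox model that yields protective efficacy. Specify the enrollment-visit sample, since day 0 follows drug clearance, and state which assay defines positive; RT-PCR is the more sensitive.
- Base the two Holm-adjusted dose comparisons on that model, or on a logrank test stratified by the same variable. Choose one in advance.
- Keep the unadjusted logrank test and hazard ratio as a sensitivity analysis.
- Give a rule for a missing enrollment RT-PCR: use the smear result or a missing category.

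The cost is SAP wording; the samples are already scheduled. The real downside is interpretive: the hazard ratio becomes conditional on enrollment status, and the plan should say so. As an illustration under assumed values (24-week risks 0.7 and 0.35, prevalence 30% to 50%), a large-sample simulation gives an arm-only hazard ratio of about 0.35. The conditional one is about 0.32 at a prognostic hazard ratio of 3 and about 0.27 at 5. Expressed as 1 minus the hazard ratio, efficacy would read 65% against 68% or 73%. Reporting both avoids confusion.
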